### 3.8.2 Healthcare professional data collection

The interviews carried out with health care professionals may be conducted in person or remotely using video-conferencing software, e.g., Zoom.

#### *HSC staff prior to baseline procedures*

- Screening
- Eligibility confirmation
- Informed consent

#### *HSC staff interview*

- A mutually convenient time will be sought to complete an interview. The interview will include background on the SHAPES innovation action, information on the intervention applied and demonstration of data collection (may include SHAPES front-end app interface and researcher interface).
- A semi-structured interview guide will guide the conversation which may be recorded (audio and video).
- The interview will be transcribed and thematic analysis conducted.

#### **3.8.3 Data collection tools**

Data collection for the service user will be documented on to a case report form (CRF). Paper questionnaires will form part of the CRF and the CRF will be the source for questionnaires. The source for all data points can be found in the data plan. The CRF will then be transcribed onto an online database using Microsoft Excel and analysed using Microsoft Excel and IBM SPSS Software this will be stored on NHSCT computers behind the NHSCT firewall. Specific data will be securely shared with other SHAPES partners and appropriate Data Processing Agreements will be in place.

Data collection for the interviews with healthcare professionals may be audio and visually recorded. This will be completed either by using videoconferencing software e.g., Zoom or using a Dictaphone. Interviews will be transcribed either manually or using software and the transcript validated by a second researcher.

#### **3.8.4 Adverse incidents**

It is very unlikely that any adverse incidents will occur in this pilot, however if any participant spontaneously reports an adverse incident the NHSCT policy 'Adverse Incident Management Policy (including Serious Adverse Incidents)' NHSCT/17/1102 will be followed. This includes reporting to external parties if applicable, e.g., Northern Ireland Adverse Incident Centre.

Adverse incident definition: *Any event or circumstances that could have or did lead to harm, loss or damage to people, property, environment or reputation arising during the course of the business of a HSC organisation/Special Agency or commissioned service.*

If the research team are notified of a product recall regarding the devices used in this pilot the participant will be notified as soon as practicable and requested not to use the device. Arrangements will be made to physically remove the device and replace it if possible.

Clinicians will not have access to the data collected and participant treatment will not be changed due to taking part in this pilot. This is clearly noted in the participant information sheet. If participants are concerned in any way about the readings on their devices, they are to follow their normal mechanisms for seeking healthcare.

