Participants will receive one-on-one, face-to-face introduction to the app and training on how to use both it and the connected medical devices. A user manual will contain detailed step-by-step supportive guidance and information, and will be provided to participants in hard-copy format for reference by participants during the pilot. There will be a run-in period of approximately one week wherein the participant can familiarise themselves with the app and liaise with the researchers to troubleshoot any problems they may be experiencing with the technology. Participants will be asked to use the app and connected devices for 12 weeks. Researchers will contact participants by telephone at the end of week 1, if there are three or more consecutive days where no data has been received (up to a maximum of four times during the pilot) and monthly (if required) thereafter. These telephone contacts are to enable the researchers to support participants with their use of the technology and troubleshoot any issues they may be experiencing (no health advice or clinical support will be provided by the researchers. If participants have any health concerns they will be encouraged to contact their specialist care team).

All data entered or transferred into the SHAPES app (i.e., clinical readings, survey responses) is pseudonymised and will be stored in the technical partners' (EDGE and GNOMON) servers and then uploaded to the SHAPES big data platform. Selected data is then processed by two further SHAPES digital solutions; a heart failure decompensation risk prediction algorithm (VICOM) and an analytic tool that generates personalised dynamic thresholds for participants' clinical parameters (TREE). These digital solutions have not yet been validated or CE-marked for use as medical devices. Therefore, the outputs will not be used to inform clinical care, but rather to determine whether the digital solutions are capable of producing outputs reliably using the available data, and to indicate if there are any associations between the risk scores generated and the participants' use of unscheduled care.

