Participants' data and outputs from VICOM and TREE digital solutions will be uploaded to a browser-based researcher dashboard. Researchers will be able to view each participant's clinical and survey data, and manage participants' medication regimens as needed. Researchers will view the available data and information for purposes of monitoring usage of the app and inputting changes to medication regimens only.

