| Baseline Questionnaires ( Barthel Index; EHFS; Gijon Scale; MARS; BMQ; EQ-5D-5L; GSES; OSSS-3; HLM1; participation measure; WHOQOL-BREF ) Medical history data; Demographic data; Technical data; Laboratory results; Unscheduled care; Current prescribed medication   |                |                 | X              |                   |                            |   |                                   |                |
| During pilot ( collected via SHAPES app ) Blood pressure, heart rate, oxygen saturation, weight (daily); Blood glucose (as directed); Heart failure symptom survey (daily); MARS questionnaire (weekly); Unscheduled care updates (as they occur); Prescribed medication updates (weekly); SHAPES app tracking data (continuous); Adverse events; Contact with researchers. |                |                 |                | X                 |                            |   |                                   |                |
| End of pilot Questionnaires ( UEQ-S; SUS; MARS; BMQ; EQ-5D-5L; GSES; OSSS-3; HLM1; participation measure; WHOQOL-BREF; technology acceptance measure ); Demographic data.   |                |                 |                |                   | X                          |   |                                   |                |
| Participant interview  |                |                 |                |                   |                            | X   |                                   |                |
| 3-month follow-up Questionnaires ( EQ-5D-5L; GSES; OSSS-3; HLM1; participation measure; WHOQOL-BREF )   |                |                 |                |                   |                            | X   | X                                 |                |
| HSC Health and social care; EHFS European Heart Failure Self-Care Behaviour Scale; MARS Medication Adherence Report Scale; BMQ Beliefs about Medicines Questionnaire; GSES General Self-Efficacy Scale; OSSS-3 Oslo Social Support Scale-3; HLM1 Single-item Health Literacy Measure; WHOQOL-BREF Abbreviated World Health Organisation Quality of Life questionnaire                     |                |                 |                |                   |                            |   |                                   |                |

Figure 1: Service user participant timeline

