##### *Service user baseline procedures*

- Questionnaires — Barthel Index, Gijon Scale, EHFS, MARS, BMQ, EQ-5D-5L, GSES, OSSS-3, HLM1, participation measure, WHOQOL-BREF
- Medical history data — height, weight, left ventricular ejection fraction, heart rhythm, implanted devices, medical conditions, heart failure stage, dyspnoea level, smoking status, leg pain symptom question
- Demographic data — including DOB, education, sex, marital status, occupational status, caregiver status, housing details
- Technical data — device monitoring details e.g. model, manufacturer, serial number and preferred time of day for reminders/questionnaires, make and model of the participants own smartphone/tablet
- Laboratory results — urea, creatinine, sodium, potassium, haemoglobin, cholesterol, eGFR, HbA1c, ACR, urine creatinine, urinary albumin-creatinine ratio
- Unscheduled care — hospitalisations (previous 3 months), and previous month hospital readmissions, A&E attendances, out of hours care, specialist service contacts, emergency ambulance call outs

- Current prescribed medication — name, frequency, strength, chronic or as required, stop date if stopped during the pilot, start date if started during the pilot.

*Service user study visits and procedures*

- During the pilot, the participant will be asked to record the following at least once daily, as appropriate, via the SHAPES app; blood pressure, heart rate, oxygen saturation, weight (which will include body mass index, body fat, visceral fat, skeletal muscle, basal metabolic rate).
- Participants diagnosed with diabetes and monitoring blood glucose regularly will be requested to record their blood glucose with the same frequency as directed by their doctor on the SHAPES app.
- Participants diagnosed with heart failure will be asked a series of daily questions about their heart failure symptoms administered via the SHAPES app.
- All participants will be asked about their adherence to medication with a weekly MARS questionnaire administered via the SHAPES app.
- During the pilot, the patient may view their medication list
- Unscheduled care updates — any updates to baseline hospitalisations, hospital readmissions, A&E attendances, out of hours care, specialist service contacts, emergency ambulance call outs recorded from medical notes
- Prescribed medication updates — any updates to prescribed medications notified by participant

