- Tracking data — log data on how the participant uses the SHAPES app e.g., date/time of usage, what functionalities were accessed
- Adverse events — date, start time, injury description, incident description, action taken, location of incident (private home or healthcare facility)
- Researchers will document any contact received/provided regarding support required to facilitate the pilot (date, duration, reason)

*Service user end of pilot visit (+14 days)*

- Questionnaires — UEQ-S, SUS, MARS, BMQ, EQ-5D-5L, GSES, OSSS-3, HLM1, participation measure, WHOQOL-BREF, technology acceptance measure
- Participant may participate in an interview at this time or a separate date may be accommodated.
- Demographic data — marital status, occupational status, caregiver status, housing details

*Service user follow-up study visits and procedures*

- If an interview is to be conducted this may occur at a mutually convenient time after the intervention has been completed.
- 3 month follow-up data collection (+/- 7days):
- Questionnaires — EQ-5D-5L, GSES, OSSS-3, HLM1, participation measure, WHOQOL-BREF

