#### 4.4 End of pilot and termination criteria

The pilot will be stopped if there is evidence of harm caused to participants due to their involvement in the pilot e.g., data breach or device malfunction.

The end of pilot will be defined as the last participant, last follow-up.

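### Section 3.8.4 acts on adverse incidents only when a participant volunteers one, nobody is described as asking, and Figure 1 labels the same data as app-collected, so minor harms and near misses may go unseen

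*Protocol*

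**What the plan says.** Four places in the protocol bear on how harm is captured.

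- **Section 3.8.4 (Adverse incidents)** calls incidents very unlikely and applies the Trust's incident policy "if any participant spontaneously reports an adverse incident". The definition it adopts is broad and includes circumstances that might have caused harm but did not.
- **Section 3.5 (Figure 1)** has a row for the pilot period marked "collected via SHAPES app". Its items include "SHAPES app tracking data (continuous); Adverse events; Contact with researchers".
- **Section 3.8.1 (study visits and procedures)** lists the fields to record: "Adverse events — date, start time, injury description, incident description, action taken, location of incident (private home or healthcare facility". It gives no question, source or frequency.
- **Section 4.4** states: "The pilot will be stopped if there is evidence of harm caused to participants due to their involvement in the pilot". It offers a data breach and a device malfunction as examples, and it is the only stopping criterion given.

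**The concern.** The protocol does not give one clear account of how harm comes to the team's notice. Section 3.8.4 describes a passive method. Figure 1 suggests an app route that is not described elsewhere. Section 3.8.1 sets out a record without saying what prompts anyone to open it. The terms differ as well: section 3.8.4 defines an adverse incident, while Figure 1 and section 3.8.1 refer to adverse events, which are not defined or tied to that definition.

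Two things are at stake. First, if few or no incidents are recorded, a reader cannot tell whether little happened or nobody was asked. Secondly, the stopping criterion needs evidence of harm, and part of that evidence depends on participants recognising a problem and choosing to mention it. Safe use of medicines at home is also among the secondary objectives in section 2.3, so incident information bears on what the pilot sets out to show.

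**Working it through.** No figure is involved, so the check sets the sections side by side and asks of each whether it leads anyone to ask about harm or brings harm to incident review.

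1. **App entries (section 3.3).** Participants supply device readings, a daily heart failure survey where applicable, a weekly medicines survey and weekly notice of treatment changes. No adverse event entry is described, so the Figure 1 label has nothing behind it in the text.
2. **Telephone contacts (sections 3.3 and 3.8.6).** Calls are made at the end of week 1, after three days without data (at most four times), and monthly if needed. Their stated purpose is technical: "These telephone contacts are to enable the researchers to support participants with their use of the technology". Neither section has the caller ask about injury or harm. Section 3.3 says the no-data calls will be made, while section 3.8.6 says only that they may be.
3. **Dashboard (section 3.3).** "Researchers will view the available data and information for purposes of monitoring usage of the app and inputting changes to medication regimens only". This is not a safety review.
4. **Medical notes (section 3.8.1).** Updates on unscheduled care, from hospitalisations through to "specialist service contacts, emergency ambulance call outs recorded from medical notes", reach researchers whether or not the participant says anything. They are collected as utilisation data. Nothing sends them to incident review or to the stopping criterion.
5. **Other routes (sections 3.8.4 and 4.4).** A product recall comes to the team by notification. A data breach can be found without a participant report, and a device malfunction may show as missing data on the portal.

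| Kind of event | Stated route other than a volunteered report | Linked to incident review |
|---|---|---|
| Event leading to unscheduled care | Medical notes | Not stated |
| Data breach or recall | Can surface independently | Recall: handled in 3.8.4; breach: named as an example in 4.4 |
| Device malfunction | May show as missing data, prompting a technical call | Named as an example in 4.4 |
| Minor injury or problem with a device that still transmits | None described | Volunteered report only |
| Near miss, such as an error in the uploaded medication list noticed before any harm | None described | Volunteered report only |

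The last two rows are the gap. Both fall within the definition that section 3.8.4 adopts, and near misses are the kind of event a participant may not recognise as reportable.

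**The case against.** The strongest reply is that section 3.8.4 says what happens when an incident is volunteered and does not say that this is the only route. Section 3.8.1 lists adverse events among the study procedures with structured fields, and events serious enough to need unscheduled care appear in the notes regardless. That stands as far as it goes: a reader might infer that no harm can reach the team unless a participant speaks up, and the protocol does not support that. It does support the narrower statement that spontaneous report is the only trigger given in section 3.8.4 and that no section describes anyone asking.

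Three other stronger readings also fail.

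- **That the stopping criterion depends entirely on volunteered reports.** Its own examples can come to light in other ways.
- **That people who stop using the app are lost to view.** Three days of silence is itself a reason for a call, and the review of notes does not depend on app use. What remains is that the call is not stated to cover harm.
- **That Figure 1 sets up a deliberate second capture route.** The same row holds contacts with researchers, which researchers document, and unscheduled care, which comes from notes. The app label is therefore loose and may be no more than a labelling error. It still has to be reconciled with section 3.8.4.

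It can also be said that this is a 30-person engagement pilot of CE-marked devices, with no safety outcome, algorithm outputs that do not inform care, and treatment that participation does not change. This limits how much harm is plausible, and so the weight of the point. It does not explain why adverse events are listed for collection with no method of finding them. Finally, section 3.8.3 refers to a data plan for the source of every data point. That plan is not at hand and may name a source for adverse events, but it would not remove the inconsistency within the protocol.

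**Conclusion.** The point holds as a gap in ascertainment and an inconsistency of wording. Section 3.8.4 gives a passive trigger, no section describes participants being asked, and Figure 1 and section 3.8.1 do not supply the missing method. The events most exposed are minor injuries, device-related problems and near misses. Events leading to unscheduled care are seen but not linked to incident review. The information behind the stopping criterion is therefore incomplete in part.

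The size cannot be put as a number. The protocol states no expected incident rate and no rate at which participants report, so any count of missed incidents would be invented. The conclusion assumes that the description of app entries in section 3.3 is complete and that the calls are confined to the purpose stated for them. If the data plan or a call script already includes a question about harm, only the reconciliation of wording remains. The change is worth making because it is cheap and strengthens the safety information; the point does not call the pilot's design into question.

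**What to change.** Add one fixed, neutral question about any problem or injury related to the app or devices. Ask it at the week-1 call, at any later call and at the end-of-pilot visit, and record the answer on the CRF each time, including when the answer is none. With 30 participants and two scheduled contacts each (week 1 and end of pilot), this gives up to 30 × 2 = 60 recorded answers before any further calls are counted. A low count can then be read against the number of times the question was asked.

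Make section 3.8.4, section 3.8.1 and Figure 1 state the same capture route, use one term for the event, and correct the Figure 1 label if the app is not the source. Say also whether unscheduled care found in the notes is looked at for possible incidents.

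The cost is one CRF item at contacts that already exist, with no extra visits or staff, and a few more minor incidents to log. The question will not reach a participant who cannot be contacted, so missed contacts should be visible on the CRF and not read as an answer of none.

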### 3.8.5 Risks to research staff

To minimise risks to researchers, the NHSCT policy 'Lone Worker' NHSCT/12/471 will be followed and appropriate personal protective equipment will be used by researchers on home visits to participants.

### 3.8.6 Protocol deviations

Data collection will be monitored by the research team through the researcher web portal. Participants will be contacted via phone after a week of starting the intervention to see if they need any assistance. Thereafter the participant will be encouraged to contact the research team if they are having any technical difficulties. If no data are uploaded for 3 consecutive days the research team may contact the participant to see if there is a technical issue, this may occur a maximum of 4 times during the pilot. Additionally, if there are significant issues with data collection, participants may be contacted monthly to act as a reminder or to troubleshoot any issues that may occur. If the participant notifies researchers via the app that there is a change to their medication, the participant will be contacted to confirm the change and the app will be updated by researchers.

This pilot is examining the real world use of the SHAPES app and associated clinical devices therefore if participants do not enter data as requested in the pilot this will not be documented as a protocol deviation, rather this will provide an insight into the usability of this digital solution.

### 3.8.7 Data management

Data processed in this pilot will be subject to the Data Protection Act 2018. This is the UK's implementation of the General Data Protection Regulation (GDPR). The NHSCT will be the data controller for all data collected during this pilot. The data flow for this pilot is complex (see figure 2) and as such multiple Data Processing Agreements will be put in place between the data controller (NHSCT) and each SHAPES partner who processes this data.

Personal data minimization and purpose limitation principles have been followed so that this pilot will only process data that is adequate, relevant and limited to what is necessary to deliver the objectives of the pilot. Personal data may be processed only for these purposes. Only personal data strictly necessary to the completion of this pilot will be retained.

The data collected for this pilot will be contemporaneous and accurate. If a participant withdraws from the study, clarification will be sought as to what data may need to be erased. This data will be identified and erased without delay. Personal data will be de-identified at the end of the SHAPES Innovation Action (Oct 2023). The NHSCT de-identified data set may be retained for a period of five years after October 2023 and then deleted. An anonymous, aggregated dataset will be stored indefinitely for future use by researchers. A de-identified, dataset may be shared with other SHAPES partners if an appropriate data sharing agreement is in place.

The data for this pilot will be stored securely. The location of each data point is listed in the data plan for this pilot, this document is a working document and will be kept up to date. Personal data will be kept in a form which permits identification of data subjects by approved NHSCT staff until October 2023.

All data in this pilot is traceable using the pilot data plan. This means that the research team are able to identify the origin of the data, how it's processed, where stored and if it has been transferred or disclosed to a third party.

Further details regarding personal data are described in the Data Protection Impact Assessment (DPIA), Personal Data Processing Descriptions document and DPIA risk assessment document for this pilot. Additionally, a detailed description of all data (including but not limited to personal data) collected can be located in the data plan for this pilot.

[figure not shown]

Figure 2: PT3-gen data flow/architecture diagram

